### Prior to exit from the clinical unit

Subjects will be allowed to leave the clinical unit 72 hours post-OZ439 and PQP treatment at the Investigator's discretion.

The following procedures will occur prior to discharge from the clinical unit:

1. Perform symptom-directed physical examination at Investigator's discretion
2. Record vital signs.
3. Collect blood samples for haematology, biochemistry (including CRP biomarker), PK analysis and malaria 18S qPCR - 72 hours post-OZ439 and PQP dosing.
4. Obtain 12-lead ECG in triplicate
5. Record AEs and use of concomitant medications.

Out-patient monitoring post-OZ439 and PQP treatment (Day 12 up to Day 42±2)

Follow-up at either AM (approximately 08:00) or AM and PM (if necessary, approximately 12 hours apart) will be undertaken on an out-patient basis through visits post confinement for clinical evaluation and blood sampling.

The following procedures will take place during these visits:

1. Elicit information regarding any new medical conditions or illnesses.
2. Collect a blood sample for malaria 18S qPCR in the morning and in the evening on days 12 and 13 and then three times weekly or at Investigator's discretion based on parasitaemia until Day 42±2.
3. Collect blood samples for parasite lifecycle stage qPCR at the Investigator's discretion (Section 7.2.2).
4. Collect blood samples for PK analysis of OZ439 and PQP at 2, 96±48, 240±48, 336±48, 504±48, 672±48 and 840±48 hours after OZ439 and PQP administration.
5. Collect blood samples for haematology and biochemistry (including CRP biomarker) and urine for urinalysis at 336±48, 504±48 and 672±48 hours post-OZ439 and PQP administration or at the Investigator's discretion.
6. Collect optional blood samples for complement regulatory protein (if consented separately) at 96±2, 120±48, 168±48, 240±48 hours post-OZ439 and PQP.
7. Collect optional blood samples for immune cell characterisation (if consented separately) at 168±48 hours post-OZ439 and PQP.
8. Perform symptom-directed physical examination when signs or symptoms of malaria are identified and it is clinically indicated.
9. Record vital signs.
10. Record malaria clinical score if vital signs are abnormal or at Investigator's discretion.
11. Record AEs and use of concomitant medications.
12. Check subject diaries.

Rescue treatment with Riamet®

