Percentage of subjects with recrudescence of parasitaemia. The percentage of subjects with recrudescence of parasitaemia following treatment with OZ439 and PQP will be determined by the number of subjects who experience recrudescence which is defined as  $\geq 5,000$  blood stage parasites/mL and a 2-fold parasitaemia increase within 48 hours, occurrence of malaria symptoms with a malaria clinical score  $> 6$ . This will be determined by parasite lifecycle qRT PCR.

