Subjects then came to the clinical unit once daily from Day 4 until presence of asexual parasites was established by quantitative polymerase chain reaction (qPCR) targeting the 18S rRNA gene (referred to hereafter as malaria 18S qPCR). Once malaria 18S qPCR became positive and until OZ439 and PQP administration, subjects came to the clinical unit twice-daily, separated by approximately 12 hours, for clinical evaluation and blood sampling.

On day 8, subjects were admitted to the clinical unit for single dose administration of OZ439 and PQP on Day 8. Subjects were followed up as inpatients for 72 hours to ensure tolerance of the investigational treatments (OZ439 and PQP) and clinical response.

After discharge from the clinical unit, subjects were followed up regularly for safety assessments, PK sampling, clinical evaluation, and malaria 18S qPCR blood sampling until Day 42±2 (34 days after OZ439 and PQP co-administration). All subjects received a standard course of Riamet® (artemether-lumefantrine) on Day 42±2, or earlier in the event of failure of clearance or recrudescence of parasitaemia or at Investigators discretion based on subject safety. For guidance, the definitions for failure of parasite clearance and recrudescence are provided.

- **Failure of parasite clearance:** failure to clear parasitaemia by at least 10-fold at 72 hours post-IP administration
- **Recrudescence:** defined as participants who showed substantial increases in parasitaemia after the initial clearance and were treated with a standard course of Riamet® to clear parasites.

The clinical judgement was made based on serial samples to ensure participant safety. Guidelines for increasing parasitaemia following initial clearance were a 2-fold parasitaemia increase from previous sample and parasitaemia exceeding the

	STATISTICAL ANALYSIS PLAN	QP17C19
		Page 12 of 53

clinically safe threshold (e.g. ≥ 5000 blood stage parasites/mL), or re-occurrence of malaria symptoms with a malaria clinical score >6 . However clinical judgement and practicality were overriding criteria for rescue treatment.

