2.3 STUDY ENDPOINTS

Primary endpoints:

- The PK/PD relationship between OZ439 and PQP plasma concentrations and blood stage asexual parasitaemia will be determined by PK/PD modelling of:
 - OZ439 plasma concentration over time
 - PQP plasma concentration over time
 - Parasitaemia profile over time, following treatment administration

The following parameters will be estimated from the PK/PD model:

- Effect of OZ439 on Emax and EC50 of PQP
- Effect of PQP on Emax and EC50 of OZ439

The following PD endpoints will be predicted from the PK/PD model:

- Time to recrudescence defined as the time at which parasite levels re-occur after being BLQ or the time for which parasitaemia levels are minimum, or, if not defined, the last observed time point without recrudescence.
- ACPR28 defined as the fraction of patients for which no parasitaemia is observed at Day 28 after drug administration,
- The incidence, severity and relationship to OZ439 and PQP of observed and self-reported AEs after the co-administration of single doses of OZ439 and PQP to healthy subjects inoculated with IBSM.

	STATISTICAL ANALYSIS PLAN	QP17C19
		Page 13 of 53

Secondary endpoints:

- Estimation of OZ439 and PQP PK parameters after co-administration of single doses using non-compartmental methods: AUC_{0-168h} , AUC_{last} , AUC_{0-inf} , C_{max} , t_{max} , $t_{1/2}$, t_{lag} , C_{168h} , CL/F , Vz/F and λ_{inf} .
- The effect of co-administered single oral doses of OZ439 and PQP on clearance of *P. falciparum* blood stage parasites from the blood of inoculated subjects as measured by qPCR up to trial Day 42±2 after co-administration of OZ439 and PQP. Parasite clearance will be assessed by the following parameters:
 - Parasite clearance half-life ($PC_{t_{1/2}}$).
 - Parasite reduction ratio (PRR).
 - Percentage of subjects with recrudescence of parasitaemia, defined as ≥ 5000 blood stage parasites/mL and a 2-fold increase within 48 hours, or re-occurrence of malaria symptoms with a malaria clinical score >6).

Exploratory objectives for the study, including presentation of endpoints, analysis methods and results, will be addressed separately, outside of the main clinical study report (CSR).

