Post-hoc pair-wise comparisons can be calculated using the test statistic $Z_G = \frac{G}{\sqrt{v_G}}$, where G is the contrast ($G = c_1 \bar{\beta}_1 + \dots + c_j \bar{\beta}_j$) and v_G is the variance of the contrast ($v_G = \frac{c_1^2}{w_1} + \dots + \frac{c_j^2}{w_j}$). The p-value of the L pair-wise comparisons will be calculated using the Scheffe method, by comparing Z_G^2 to a chi-squared distribution with $L - 1$ degrees of freedom.

Recrudescence

Recrudescence will be defined as subjects who show substantial increases in parasitaemia after the initial clearance and are treated with a standard course of Riamet® prior to the compulsory scheduled timepoint for Riamet® treatment.

PD Parameters Analysis

All PD parameters will be listed. Summary statistics will be produced by dose group. For continuous data, the number of observations, mean, SD, median, minimum and maximum values will be reported. The number and percentage of subjects will be reported for incidence data.

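### SAP 8.4 counts recrudescence by an early decision to give Riamet, whereas SAP 2.3 and the protocol define the same secondary endpoint by measurement

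*SAP*

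**What the plan says.** SAP 2.3 lists the secondary endpoint as "Percentage of subjects with recrudescence of parasitaemia, defined as ≥ 5000 blood stage parasites/mL and a 2-fold increase within 48 hours, or re-occurrence of" symptoms with a malaria clinical score above 6. Protocol 4.2.2 and 10.3.3 give the same rule. None of these three places makes treatment part of the definition.

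SAP 8.4, under Recrudescence, states the rule for the analysis: "Recrudescence will be defined as subjects who show substantial increases in parasitaemia after the initial clearance and are treated with a standard course of" the rescue drug Riamet. That course must also come "prior to the compulsory scheduled timepoint for Riamet® treatment". The section gives no parasite threshold, no time window and no clinical-score route.

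SAP 2.1 also ties recrudescence to a substantial rise after initial clearance plus Riamet, and then adds pointers: "Guidelines for increasing parasitaemia following initial clearance were a 2-fold parasitaemia increase from previous sample and parasitaemia exceeding the" level regarded as safe, with 5000/mL as the example, or returning symptoms with a score above 6. It closes: "However clinical judgement and practicality were overriding criteria for rescue treatment". The same section describes the study as open label.

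SAP 1.1 lets the SAP override the protocol where they differ. It does not say which of two SAP sections prevails.

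**The concern.** The reported percentage will follow SAP 8.4, because that section defines the variable and feeds the PD summary by dose group. A reader of the clinical study report will assume that it is the endpoint in SAP 2.3. One rule depends on what was measured. The other depends on what was measured and on whether someone decided to treat before a given day.

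Such a treatment decision can be sound care and still be a poor outcome variable. It cannot be reproduced from the qPCR and score data alone, and in an open-label study it is made by people who may know the dose. With groups of 2 to 4 subjects, a single classification changes the displayed result a great deal.

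**Working it through.** No expected recrudescence rate, power or alpha is given for this endpoint, so there is no planned figure to reproduce. The check sets the two rules against possible subject histories and then sizes one disagreement.

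**Step 1: the rules side by side**

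| Subject history after initial clearance | SAP 2.3 | SAP 8.4 |
|---|---|---|
| Meets the count and 2-fold criteria mid-follow-up, Riamet given early | counted | counted |
| First meets them on the sample taken before scheduled Riamet (Day 42±2) | counted | not counted |
| Symptoms return with score above 6, no substantial rise in counts | counted | not counted |
| Counts rise but stay below 5000/mL, score not above 6, Riamet given early on judgement | not counted | counted if the rise is called substantial |
| Reaches 5000/mL, but the doubling is seen only over more than 48 hours, score not above 6, Riamet given early | not counted | counted |
| Riamet given early for failure of clearance, no later rise, score not above 6 | not counted | not counted |

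The rules disagree in four of these six histories, two in each direction. The last row shows that early Riamet alone does not make a subject a case under SAP 8.4. The compulsory timepoint also has a window of ±2 days, so SAP 8.4 does not settle whether Riamet on Day 40 counts as early.

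**Step 2: size of one disagreement**

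Group sizes come from SAP 2.1: four groups of 2 in Cohort 1, two groups of 4 in Cohort 2 and two groups of 4 in Cohort 3. The total is 4×2 + 2×4 + 2×4 = 24, which agrees with SAP 2.4. One reclassified subject moves a percentage by 100/n points:

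- Cohort 1 group: 100/2 = 50 points
- Cohort 2 or 3 group: 100/4 = 25 points
- 1D and 3A together, if pooled as SAP 8.4 does for the PRR comparisons: 100/(2+4) = 16.7 points
- All subjects: 100/24 = 4.2 points

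**Step 3: can the 48-hour window be assessed?**

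Protocol 7.3.3 takes 18S samples in the morning and "in the evening on days 12 and 13 and then three times weekly", or at the investigator's discretion based on parasitaemia. Three samples a week average 168/3 = 56 hours apart. An evenly run week gives gaps of 48, 48 and 72 hours (sum 168), so two of three consecutive pairs fit the window. Protocol 7.3.6 also allows unscheduled qPCR visits.

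The rule can therefore usually be assessed, but not always on scheduled samples. If growth is log-linear (an assumption), a 2-fold rise over 72 hours corresponds to 2^(48/72) = 1.59-fold per 48 hours. The wording in SAP 2.1, which compares with the previous sample, is then somewhat looser than SAP 2.3.

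**Step 4: which assay?**

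Protocol 10.3.3 says of recrudescence: "This will be determined by parasite lifecycle qRT PCR". Protocol 7.2.2 makes that assay discretionary, while parasitaemia is monitored by 18S qPCR. SAP Section 8 builds PD parameters on processed parasitaemia but does not name the assay for this endpoint.

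**The case against.** The case for leaving the text alone has real substance.

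- **Rescue guidance uses nearly the same criteria.** Most subjects who meet them before Day 42 would be rescued early and counted under both rules. This stands, and it narrows the missed cases mainly to those who first qualify around Day 42 or by score alone. It does not remove the opposite error.
- **The word substantial is not left bare.** SAP 2.1 uses the same phrase and gives numeric pointers. This also stands, but the pointers are expressly non-binding and SAP 8.4 does not refer to them.
- **The endpoint is secondary and descriptive.** The 18S data, rescue doses and recrudescence status are all listed by subject, so a careful reader could check most classifications. True, but the tabulated percentage would still carry the wrong definition.

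A reader might infer four stronger things that the documents do not support:

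- That the SAP 2.3 rule cannot be applied on the visit schedule. Step 3 shows that it can, with occasional gaps above 48 hours.
- That SAP 2.1 hides a change of definition. It states its wording openly and agrees with SAP 8.4.
- That the rule was relaxed because of results seen. The SAP describes Cohort 3 doses chosen from Cohort 1 and 2 data, which dates the text but shows no motive.
- That the model-predicted time to recrudescence, which has its own definition in SAP 2.3, is a further conflict. It is a separate predicted endpoint, used in SAP 9.4 to compare simulations with patient data.

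**Conclusion.** The conflict is real and lies inside the SAP, so the precedence clause does not resolve it. If SAP 8.4 is followed, the reported percentage is not the endpoint stated in SAP 2.3 and the protocol.

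The documents hold no outcome data. The two percentages could coincide, and nothing shows that judgement differed by dose or cohort. The figures in Step 2 are the effect of one discordant subject if there is one; they do not estimate a bias. They assume the planned group sizes, with every subject in the denominator.

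This should be corrected before database lock, because the endpoint is otherwise ambiguous. It does not threaten the primary objectives.

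**What to change.** These changes are for analysis only. None of them touches when rescue is given.

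1. In SAP 8.4, derive the percentage from 18S qPCR and clinical score by the SAP 2.3 criteria. Apply them after initial clearance, up to and including the pre-Riamet sample, whether or not and whenever Riamet was given.
2. Define initial clearance for this purpose, and keep the requirement that symptoms return. Without both, a fluctuation soon after dosing, or symptoms persisting in a subject dosed early for a score above 6, could be counted. The definition should also cover subjects whose counts never become undetectable.
3. Apply a gametocyte rule consistent with SAP 9.3, since total 18S counts can include gametocytes.
4. Report subjects given Riamet early for rising parasitaemia without meeting the criteria as a separate category. Add two sensitivity analyses: (a) count them as recrudescent; (b) where the sampling gap exceeds 48 hours, judge the 2-fold rise against the previous sample, as in SAP 2.1.
5. State in the SAP that the endpoint rests on 18S qPCR. Under SAP 1.1 this governs the analysis, so the qRT-PCR sentence in protocol 10.3.3 needs no protocol amendment for this purpose.
6. Note one limitation: outpatient clinical scores are recorded only if vital signs are abnormal or at the investigator's discretion, so the score route is incompletely observed.

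Separately, the sponsor should reconcile the rescue and recrudescence wording in SAP 2.1, SAP 8.4 and the protocol. This review takes no view on which clinical rule is right.

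The cost is a few SAP paragraphs and reprogramming one derived variable, mostly from data already collected. If the database is already locked, the same analysis can be reported as a justified deviation under SAP Section 4.

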8.5 ANALYSIS SOFTWARE

R version 3.5.0, RStudio version 1.1.447, and SAS Enterprise Guide Software version 7.12 or more recently updated versions will be used for all data processing and analyses.

8.6 REPORTING

The PD and parasitaemia results will be reported in the main text of the CSR, and will also be presented in listings, tables, and figures.

	
STATISTICAL ANALYSIS PLAN
	
QP17C19

		
Page 35 of 53

SECTION 9: PK/PD ANALYSIS

9.1 OVERVIEW

A population PKPD model will be derived from the concentrations and parasitaemia observed in the challenge volunteers. It is achieved by sequentially developing a population PK model to describe the observed individual PK profiles and a population PD model for quantifying the relationship of plasma concentrations and the parasite clearance. The model building is supported by PK/PD data from studies QP12C10 and QP13C05 for OZ439 and PQP mono treatment in healthy volunteers.

The final model will be employed to simulate patients of the OZ439 mono study 12_006 and the OZ439/PQP combo study 13_003. Predictions of the ACPR28 will be used to evaluate the predictive power of the human challenge model by comparing the simulations with the observed ACPR28 in clinical trials 12_006 and 13_003.

9.2 SOURCES OF DATA

9.3 DATA HANDLING

Data from studies QP12C10, QP13C05 and QP17C19 will be pooled. The data set will contain information on the individual OZ439/PQP doses, OZ439 PK concentrations, PQP PK concentrations, the triplicated parasitemia levels and typical covariates such as age, height, weight, sex and race.

Data assembly

First a master dataset will be assembled formatted according to the MMV dataset standard (cf., "MS_IQdataset_V1.docx"). Plasma concentrations will be in $\mu\text{g/mL}$, total parasite levels in counts/mL, and doses in mg. Parasite data after the first administration of rescue medication is flagged by setting the IGNORE column to "Observations after rescue medication". The time in hours is relative to the OZ439/PQP administration time. Total counts of parasites for which counts of gametocytes exceeded 10% of total counts are flagged to be ignored (by setting the column IGNORE to "gametocytes") If the lab providing the parasitemia data marks records as (mainly) gametocytes the values are set to half of the LLOQ.

A general analysis dataset is derived from the master dataset. The general analysis dataset will contain the following observations: OZ439 plasma concentrations, PQP plasma concentrations, and total counts of parasites. Values of replicate measurement and their geometric means are contained for the parasite counts. In addition, dosing records for *P. falciparum* inoculation, OZ439/PQP administration, and rescue medication administration will be defined. It is advised to define additional columns DOSELEVEL1 and DOSELEVEL2 to indicate the dose amounts of OZ439 and PQP a subject received as covariate columns.

	STATISTICAL ANALYSIS PLAN	QP17C19
		Page 36 of 53

Nonlinear mixed effects (NLME) datasets for the PK and PD modelling will be derived from the general dataset.

PK modelling data set

Observations below the lower limit of quantification (LLOQ) will be censored by setting the CENS column for these observation records to 1 and setting the corresponding dependent variable (DV) column to the LLOQ (→ M3 method). Observation records with missing values and records with missing times will be ignored. Records flagged to be ignored will be removed from the dataset. Observations not analysed in the PK modelling (i.e., all parasite count records) will be removed.

As a result, the PK modelling dataset only contains OZ439/PQP dosing records and OZ439/PQP plasma concentration records.

PD modelling data set

Observations below the LLOQ will be censored by setting the CENS column for these observation records to 1 and the corresponding DV value to the LLOQ, i.e., 10 p/mL (→ M3 method). Total counts of parasites for which counts of gametocytes exceeded 10% of total counts are flagged to be ignored (by setting the column IGNORE to "gametocytes"). If the lab providing the parasitaemia data marks records as (mainly) gametocytes the values are set to half of the LLOQ. Observation records with missing values and records with missing times will be ignored. Records flagged to be ignored will be removed from the dataset. Observations not analysed in the PD modelling analysis (i.e., concentration records) will be removed.

As a result, the PD modelling dataset only contains only OZ439/PQP dosing records and total parasite counts (i.e., cleaned replicate means). The total parasite counts will be log-transformed for the PD modelling and estimated individual PK model parameters will be added to the dataset as regressors. For a correct estimation of the model baseline parasitaemia value that is defined as the value at the first observation for each subject, the first observation time needs to be similar across the subject to ensure that the baseline values are at similar values. Hence, the first modelled observation time is a timepoint at which the observed parasitaemia value is available for all subjects. All previous timepoints will be removed.

	STATISTICAL ANALYSIS PLAN	QP17C19
		Page 37 of 53

9.4 METHODS

Model building

General PKPD model building approach

Population models of the PK and PD will be developed in step-wise manner.

1. An NLME model for the PK (OZ439, PQP and combinations) will be developed to obtain individual PK parameter estimates based on which the individual PK profiles are described well.
2. The PKPD population model for OZ439 mono treatment will be built sequentially. That is, a PK model will be developed first. Second, using the individual PK parameter estimates as regression parameters and estimating the PD part of the model only. Estimation of typical and individual PD parameters will first be performed with IQRtools SysFit to investigate model identifiability and second with Monolix to additionally estimate inter-individual variability (IIV).
3. The PKPD population model for PQP mono treatment will be built using the individual PK parameter estimates as regression parameters and estimating the PD part of the model only. Estimation of typical and individual PD parameters will first be performed with IQRtools SysFit to investigate model identifiability and second with Monolix to additionally estimate IIV.
4. The parasitaemia base line levels and parasite growth rate (PD parameters) in the absence of the drug will be estimated from the total parasite counts of the OZ439/PQP combo study QP17C19 before treatment. Estimation of typical and individual PD parameters will be performed with IQRtools SysFit.
5. The PKPD model for the OZ439/PQP combo study will be built using the
 - individual PK parameter estimates as regression parameters,
 - individual growth rate and base line parasitaemia values as regression parameters,
 - typical E_{max} , EC50 and Hill parameter values of OZ439 and PQP as fixed parameters from the mono PD models (Monolix),
 - IIV values for and E_{max} , EC50 of OZ439 and PQP as fixed parameters from the mono PD models (Monolix).
 - Individual PD parameters and drug-drug interaction parameters will first be estimated using IQRtools SysFit to investigate identifiability of multiple drug-drug interaction models. Second, considering the identifiability analysis, Monolix will be used to estimate individual parameters for selected models.

For both PK (NLME with Monolix) and PD (IQRtools SysFit), IIV is implemented for normally distributed parameters using the following equation with θ_0 as population average parameter, θ_i as individual parameter, and η_i as random effect that is distributed normally around zero ($\eta_i \sim N(0, \omega^2)$):

	STATISTICAL ANALYSIS PLAN	QP17C19
		Page 38 of 53

$$\theta_i = \theta_0 + \eta_i.$$

The following equation is used for log-normally distributed parameters:

$$\ln(\theta_i) = \ln(\theta_0) + \eta_i.$$

Continuous covariates on log-normally distributed parameters will be implemented as follows:

$$\theta_i = \theta_0 \cdot \left(\frac{COV_i}{COV_{median}} \right)^\beta \cdot \eta_i.$$

θ_i represents the individual parameter, θ_0 the population mean value, COV_i the individual covariate value, COV_{median} , the population median covariate value, β the covariate coefficient, and η_i the individual random effect.

	STATISTICAL ANALYSIS PLAN	QP17C19
		Page 39 of 53

Categorical covariates on log-normally distributed parameters will be implemented as follows.

$$\theta_i = \theta_0 \cdot \sum_j (e^{\beta_j \cdot COV_{ij}}) \cdot \eta_i$$

The individual covariate values COV_{ij} are 1 if subject i belongs to the j th category of the covariate and 0 otherwise. β_j is the covariate value for the j th category. For one category, i.e. the reference, β_j is 0.

For the NLME PK modelling, the log-likelihood and the Fisher information matrix will be approximated by linearization. The number of iterations in the burn-in and the accumulation phase will be 500 and 200 respectively, but might be adjusted if required based on inspection of parameter estimate and objective function traces along estimation iterations. Individual parameters will be determined as conditional modes.

For PD modelling, the IQRtools SysFit implementation using a non-linear fixed-effects modelling approach is employed. Typical and individual parameters are both treated as fixed effects. The parameterization of individual parameters and covariates is fully consistent with the NLME parameterization above. The variances ω^2 of NLME random effects are accounted for by quadratic priors, $l_{prior}(\eta) = \frac{1}{2} \frac{\eta^2}{\omega^2}$, added to the log-likelihood function, where the values for ω^2 are fixed and the η parameters are estimated.

The profile-likelihood method [RAU09, KAS16] is used to compute confidence intervals of the parameters estimated with the SysFit approach.

Model evaluation

Assessment of model adequacy and decisions about increasing model complexity will be driven by the data and guided by goodness-of-fit criteria, including

1. visual inspection of diagnostic scatter plots (observed vs. predicted concentration, residual/weighted residual vs. predicted concentration or time and histograms of individual random effects, for example),
2. successful convergence of the minimization routine with at least 2 significant digits in parameter estimates,
3. plausibility of parameter estimates,
4. precision of parameter estimates,
5. correlation between model parameter estimation errors < 0.95, and
6. the Bayesian information criterion, given the minimum objective function value and number of estimated parameters.

For the nonlinear fixed effects models, additional diagnostic plots will be produced:

7. objective function values across multiple fits from randomised initial guesses, and

	
STATISTICAL ANALYSIS PLAN
	
QP17C19

		
Page 40 of 53

8. profile likelihood plots

All parameter estimates will be reported with a measure of estimation uncertainty, such as the standard error of the estimates. The individual PK fits will be used to evaluate the adequacy to use the individual PK parameter estimates as regression parameters for PD modelling.

The adequacy of simulation with the final models will be evaluated by visual predictive checks. Visual predictive checks for each dose level will be performed by simulation of the study 200 times taking parameter estimation uncertainty into account. 95%-confidence intervals for the 5th percentile, the median, and the 95th percentile will be derived and compared to the corresponding values based on the data.

To compare simulations of the final model with patient data, both, the data and the simulation will be transformed into a life table format indicating for each individual the time of recrudescence, i.e., the time at which parasite levels re-occur after being BLQ or the time for which parasitaemia levels are minimum, or, if not defined, the last observed time point without recrudescence. The Kaplan-Meier estimator [KAP58, THE15, TER00] will be used to compare model and data.

PK modelling

The PK of OZ439/PQP will be modelled using compartmental models describing the absorption after oral administration, distribution between central and peripheral compartments, and the elimination from the central compartment. The visual data analysis will guide the selection of models that will be tested (e.g., with respect to number of compartments, linear or saturable elimination, absorption kinetics and error model).

The allometric function will be used to include the impact of weight (*WGT*) on the clearance rate (*CL*) and central compartment volume (*V_c*):

$$CL_i = CL \cdot \left(\frac{WGT_i}{WGT_{median}} \right)^{0.75}$$

$$V_{c_i} = V_c \cdot \left(\frac{WGT_i}{WGT_{median}} \right)^{1.00}$$

The same relation as for *CL* will be used for the inter-compartmental clearance rate *Q1* and, if a third compartment is required, *Q2*. The same relation as for *V_c* will be used for the peripheral volume *V_{p1}* and, if a third compartment is required, *V_{p2}*. The previous analysis of the OZ439 mono study QP12C10 (human challenge) has revealed that the dose amount might be a significant covariate for the clearance rate. The PK model is supposed to be used in simulations of patients, including children. Therefore, dose amount as covariate might not be appropriate, because the same dose

	STATISTICAL ANALYSIS PLAN	QP17C19
		Page 41 of 53

amount could lead to significantly different drug exposure, depending on the clearance that relates to weight. To correctly account for exposure, a new covariate

$$AUC = \frac{Doseamount}{Weight^{0.75}}$$

is derived from the base covariates and will be included when testing covariates. More covariates will be included if appropriate. It will be tested whether including interaction terms for the impact of one compound on the clearance of the other leads to a better description of the data.

PD modelling

As a general concept, the changes in living parasite P are modeled as the effect of a net exponential growth rate GR and a killing or clearance rate $Kill$ due to OZ439/PQP with an initial parasitemia level P_{base} at time t_0 (time of first observation). The equations are expressed on the log-scale such as

$$\frac{dPL}{dt} = GR - Kill$$

$$PL(t_0) = PL_{base},$$

where $PL = \ln(P)$ is the log-transformed parasite counts. The killing rate $Kill = Kill_1 + Kill_2$ is composed of contribution from OZ439 (index 1) and PQP (index 2). The killing rate of each drug is described by an E_{max} model. The E_{max} model assumes a direct effect of concentrations on parasite killing/clearance, such as:

$$Kill_1 = EMAX_1 \cdot \frac{Cc_1^{Hill_1}}{Cc_1^{Hill_1} + EC50_1^{Hill_1}}$$

$$Kill_2 = EMAX_2 \cdot \frac{Cc_2^{Hill_2}}{Cc_2^{Hill_2} + EC50_2^{Hill_2}}$$

Here, Cc is the concentration in the central compartment, $EMAX$ is the maximum effect of the drug, $EC50$ is the concentration that results in 50% of the maximum effect and $Hill$ is the Hill coefficient.

Two alternative models to combine the killing effect of each drug are considered. First, a so-called empirical Bliss independence approach is applied. The kill is modelled as sum of the single effects and an interaction term that is the scaled product of the single effect and an interaction coefficient γ .

$$Kill = Kill_1 + Kill_2 + \gamma \cdot \frac{Cc_1^{Hill_1}}{Cc_1^{Hill_1} + EC50_1^{Hill_1}} \frac{Cc_2^{Hill_2}}{Cc_2^{Hill_2} + EC50_2^{Hill_2}} \min(Kill_1, Kill_2)$$

Second, an additive effect of both drugs on the killing rate is assured, $Kill = Kill_1 + Kill_2$. However, the E_{max} and $EC50$ values employed in the killing contributions can be affected by the other drug. In the analysis, two drug-drug interaction models will be used to describe the effect one drug exerts on the $EC50$ and E_{max} of the other drug: a mutual and a non-mutual model.

	STATISTICAL ANALYSIS PLAN	QP17C19
		Page 42 of 53

The non-mutual model states that

$$\begin{aligned}
 EC50_1^* &= EC50_1 \left(1 + (e^{-\alpha_{21}} - 1) \frac{C C_2^{Hill_2}}{EC50_2^{Hill_2} + C C_2^{Hill_2}} \right) \\
 EC50_2^* &= EC50_2 \left(1 + (e^{-\alpha_{12}} - 1) \frac{C C_1^{Hill_1}}{EC50_1^{Hill_1} + C C_1^{Hill_1}} \right) \\
 EMAX_1^* &= EMAX_1 \left(1 + (e^{\beta_{21}} - 1) \frac{C C_2^{Hill_2}}{EC50_2^{Hill_2} + C C_2^{Hill_2}} \right) \\
 EMAX_2^* &= EMAX_2 \left(1 + (e^{\beta_{12}} - 1) \frac{C C_1^{Hill_1}}{EC50_1^{Hill_1} + C C_1^{Hill_1}} \right).
 \end{aligned}$$

Hence, the modified EC50 or E_{max} for one drug is the original value scaled by a factor that is modulated by the other drug concentration. In short, $\alpha \geq 0$ decreases the EC50 and $\beta \geq 0$ increases the E_{max} .

The mutual model assumes that $\alpha_{12} = \alpha = \alpha_{21}$ and $\beta_{12} = \beta = \beta_{21}$. Thereby, the number of interaction parameters is reduced from 4 to 2 in the mutual model.

IIV will be assumed on all parameters except the Hill coefficient and the interaction parameters. Parameters are assumed to be log-normally distributed besides the log-transformed parasite baseline value for which the normal distribution was assumed. The standard deviation of the IIV will be fixed to 0.2 for the SysFit approach. When parameters are estimated with Monolix, standard deviations of the IIV will be estimated.

Using the SysFit approach for PD modelling, parameter estimation will be started from 24 initial guesses. Identifiability of the best fit will be analysed using the profile likelihood method. In case, several local optima with similar objective value are found, those local optima will be investigated and it will be checked using modelling, if additional cohorts could help to reduce the number of local optima.

Using Monolix, optimization will be initialized with the estimated values obtained with SysFit. If optimization with Monolix poorly converges for some of the parameters as being assessed by the Monolix convergence traces, these values will be fixed to the value obtained with SysFit.

Simulations to predict ACPR28 in patients

Simulations of patients will build on the patient characteristics found in the 12_006 and 13_003 studies. Simulations will be performed as if patient PK and PD information was completely missing. Only covariates such as weight, actual dose, expected exposure and parasitaemia levels at $t = 0$ (shortly before treatment) will be used.

	
STATISTICAL ANALYSIS PLAN
	
QP17C19

		
Page 43 of 53

For each dose group, n = 200 patients will be randomly drawn with replacement. Individual parameters will be sampled from the IIV estimated by Monolix, taking covariates of the randomly chosen patients into account.

Individuals in each dose group will be simulated at densely sampled time points between 0 and 1600 hours. Initial values for the parasitaemia simulation will be fixed to the parasitaemia level of the selected patient.

The simulated time-course will be translated to a life table containing the information about the time to recrudescence. The Kaplan-Meier estimator will be used to derive the recrudescence rate at every time point and the probability of recrudescence as $(1 - \text{recrudescence rate}) \times 100\%$.

